3.2 Exclusion Criteria

- 3.2.1 Prior systemic therapy for prostate cancer (including but not limited to endocrine therapy; i.e., LHRH analogues, antiandrogens, etc.)
- 3.2.2 Evidence of metastatic disease
- 3.2.3 Prior radiation therapy for prostate cancer

- 3.2.4 Known history of allergic reactions to axitinib or other VEGF-TKIs
- 3.2.5 Presence of serious or uncontrolled infection
- 3.2.6 Major surgery <4 weeks of starting the study treatment.
- 3.2.7 Gastrointestinal abnormalities including:
 - 3.2.7.1 inability to take oral medication;
 - 3.2.7.2 requirement for intravenous alimentation;
 - 3.2.7.3 prior surgical procedures affecting absorption including total gastric resection;
 - 3.2.7.4 treatment for active peptic ulcer disease in the past 6 months;
 - 3.2.7.5 active gastrointestinal bleeding, unrelated to cancer, as evidenced by hematemesis, hematochezia or melena in the past 3 months without evidence of resolution documented by endoscopy or colonoscopy;
 - 3.2.7.6 malabsorption syndromes.
- 3.2.8 Current use or anticipated need for treatment with drugs that are known potent CYP3A4 inhibitors (ie, grapefruit juice, verapamil, ketoconazole, miconazole, itraconazole, erythromycin, telithromycin, clarithromycin, indinavir, saquinavir, ritonavir, nelfinavir, lopinavir, atazanavir, amprenavir, fosamprenavir and delavirdine). (Note: This is not a comprehensive list. For a comprehensive list of CYP3A4 inhibitors, please refer to the following link: <http://medicine.iupui.edu/clinpharm/ddis/table.aspx>; patients who are using these agents will be excluded.)
- 3.2.9 Current use or anticipated need for treatment with drugs that are known potent CYP3A4 or CYP1A2 inducers (ie, carbamazepine, dexamethasone, felbamate, omeprazole, phenobarbital, phenytoin, amobarbital, nevirapine, primidone, rifabutin, rifampin, and St. John's wort). (Note: This is not a comprehensive list. For a comprehensive list of CYP1A2 and CYP3A4 inducers, please refer to the following link: <http://medicine.iupui.edu/clinpharm/ddis/table.aspx>; patients who are using these agents will be excluded.)
- 3.2.10 Requirement of anticoagulant therapy with oral vitamin K antagonists. Therapeutic use of low molecular weight heparin is allowed.
- 3.2.11 Active seizure disorder
- 3.2.12 A serious uncontrolled medical disorder or active infection that would impair their ability to receive study treatment.
- 3.2.13 Any of the following within the 12 months prior to study drug administration: myocardial infarction, uncontrolled angina, coronary/peripheral artery bypass graft, symptomatic congestive heart failure, cerebrovascular accident or transient ischemic attack and 6 months for deep vein thrombosis or pulmonary embolism.
- 3.2.14 Known human immunodeficiency virus (HIV) or acquired immunodeficiency syndrome (AIDS)-related illness.
- 3.2.15 History of a malignancy (other than prostate cancer) except those treated with curative intent for skin cancer (other than melanoma), in situ breast or in situ cervical cancer, or those treated with curative intent for any other cancer with no evidence of disease for 2 years.
- 3.2.16 Dementia or significantly altered mental status that would prohibit the understanding or rendering of informed consent and compliance with the requirements of this protocol.
- 3.2.17 Other severe acute or chronic medical or psychiatric condition, or laboratory abnormality that may increase the risk associated with study participation or study drug administration, or may interfere with the interpretation of study results, and in the judgment of the investigator would make the patient inappropriate for entry into this study.

3.3 Inclusion of Minorities

The study is open to all participants regardless of ethnicity. Efforts will be made to extend the accrual to a representative population, but in this trial which will accrue approximately 44 patients, a balance must be struck between patient safety considerations and limitations on the number of individuals exposed to potentially toxic or ineffective treatments on the one hand and the need to explore racial and ethnic aspects of clinical research on the other. If differences in outcome that correlate to racial or ethnic identity are noted, accrual may be expanded or additional studies may be performed to investigate those differences more fully.

4.0 Screening and Registration Procedures

4.1 Screening Procedures

Diagnostic or laboratory studies performed exclusively to determine eligibility for this trial will be done only after obtaining written informed consent. Documentation of the informed consent for screening will be maintained in the patient's research chart and medical record. Studies or procedures that were performed for clinical indications (not exclusively to determine study eligibility) and within the screening window may be used for baseline values even if the studies were done before informed consent was obtained. If a patient is randomized, but ultimately does not meet the eligibility criteria for the study, he will be considered a "screen failure" and will not participate in the study. A list of screen failures and the reason for which they are considered a screen failure will be maintained.

4.1.1 Assessments within 8 weeks of the first dose

4.1.1.1 4.1.1.1 Baseline bone scan for tumor assessment

4.1.1.2 Baseline CT or MRI scan of the abdomen and pelvis

4.1.2 Assessments within 2 weeks of the first dose

4.1.2.1 Demography: date of birth, race and gender.

4.1.2.2 Medical history:

4.1.2.2.1 Prostate cancer-specific history including: date of diagnosis, current stage of cancer, prior systemic treatment for prostate cancer (an exclusion criterion); and history of other malignancies

4.1.2.2.2 Prior surgery and/or radiotherapy (date, organ/anatomic region(s) of surgery and/or radiotherapy must be documented), other significant medical and surgical histories within the past 6 months.

4.1.2.3

4.1.2.4

4.1.2.5 Physical examinations: height (only recorded at baseline) and body weight and current medical conditions.

4.1.2.6 Vital signs: body temperature, blood pressure and heart rate. **Note:** If a subject presents with poorly controlled hypertension, defined as SBP ≥ 140 mmHg or DBP ≥ 90 mmHg, antihypertensive medication(s) should be initiated or adjusted with a goal to control the blood pressure to $< 140/90$ mmHg.

4.1.2.7 ECOG PS

- 4.1.2.8 Clinical laboratory assessments, as listed on the study calendar.
- 4.1.2.9 Verification of an operative date for prostatectomy/pelvic lymph node dissection that allows for the 28 day therapeutic period as well as a 48 hour washout period prior to surgery. Prostatectomy may be performed via any accepted methodology (open, laparoscopic, robotic-assisted, etc.). Notably, standard wait times for prostatectomy at City of Hope vary between 5-6 weeks from the time of biopsy confirmation of prostate cancer. Thus, it is not anticipated that the current protocol will delay standard of care therapies on the control or experimental arms.
- 4.1.2.10 Randomization to either surgery alone or preoperative axitinib therapy, to be performed by the designated study biostatistician

4.1.3 Pre-dose Assessments on Day 1 for patients randomized to axitinib (Note: Day 1 for patients randomized to axitinib treatment is considered the first day of axitinib therapy, whereas Day 1 for patients randomized to observation will represent the date of surgical intervention. Thus, the observation period reflects the time elapsed between the date of consent and the date of surgery.)

- 4.1.3.1 Physical examination: to identify any changes in the subject's mental and medical conditions since baseline assessment that would make him/her ineligible for the study.
- 4.1.3.2 Blood pressure measurements: subjects must have a blood pressure reading of <140/90mmHg to be eligible. If anti-hypertensives were initiated and/or dosing has been adjusted during the Baseline Period, the blood pressure must be reassessed on two occasions consecutively that are separated by a minimum of 1 hour. The mean SBP/DBP values from both blood pressure assessments must be <140/90mmHg in order for a subject to be eligible. These two assessments must also be the most recent ones prior to treatment (the blood pressure values from the later assessment will be used as the subject's baseline blood pressure values).
- 4.1.3.3 ECOG PS.
- 4.1.3.4 Record all the medication(s) received within 2 weeks prior to the first dose of study medication and indicate if the medication is continuing.
- 4.1.3.5 Obtain archived tumor tissue samples for biomarker assessments.

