3.0 Patient Eligibility

3.1 Inclusion Criteria

3.1.1 Histologically confirmed diagnosis of prostate cancer

- 3.1.2 High-risk prostate cancer as defined by 1 of the 3 following criteria: (1) baseline PSA > 20, (2) clinical stage \geq T3a, and (3) Gleason score 8-9.
- 3.1.3 Subjects must be appropriate candidates for prostatectomy and pelvic lymph node dissection, as deemed by a multidisciplinary team. Subjects must provide informed consent to these procedures prior to initiating study treatment
- 3.1.4 Subjects must provide written informed consent prior to performance of study-specific procedures or assessments, and must be willing to comply with treatment and follow-up. Procedures conducted as part of the subject's routine clinical management (e.g., blood count, imaging study) and obtained prior to signing of informed consent may be utilized for screening or baseline purposes provided these procedures are conducted as specified in the protocol.
- 3.1.5 Adequate organ function as defined by the following criteria:
 - 3.1.5.1 absolute neutrophil count (ANC) \geq 1500 cells/mm³;
 - 3.1.5.2 platelets \geq 100,000 cells/mm³.
 - 3.1.5.3 Hemoglobin \geq 9.0 g/dL.
 - 3.1.5.4 AST and ALT \leq 2.5 x upper limit of normal (ULN);
 - 3.1.5.5 Total bilirubin \leq 1.5 x ULN;
 - 3.1.5.6 Serum creatinine \leq 1.5 x ULN or calculated creatinine clearance \geq 60 mL/min;
 - 3.1.5.7 Urinary protein <2+ by urine analysis (UA). If UA is \geq 2+ for protein then a 24-hour urine collection can be done and the patient may enter only if urinary protein is <2 g per 24 hours.
- 3.1.6 Male patients, age \geq 18 years.
- 3.1.7 ECOG performance status of 0 or 1.
- 3.1.8 Life expectancy of \geq 12 weeks.
- 3.1.9 No prior systemic therapy for prostate cancer
- 3.1.10 No evidence of preexisting uncontrolled hypertension as documented by 2 consecutive blood pressure readings taken within 1 hour. The baseline systolic blood pressure readings must be \leq 140 mm Hg, and the baseline diastolic blood pressure readings must be \leq 90 mm Hg. Patients whose hypertension is controlled by antihypertensive therapies are eligible.

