5.1 Registration Requirements/Process

To register a patient, the treating physician should contact the protocol nurse or the responsible Clinical Research Associate (CRA) in Clinical Trial Office (CTO) to complete the eligibility/registration form. The protocol nurse or CRA will contact the Data Coordinating Center at the City of Hope [contact], [name] or e-mail [contact]), EMAIL a copy of the completed eligibility checklist, required pre-study tests (per protocol – and may include laboratory, CT and pathology reports), signed Informed Consent, signed Patients' Bill of Rights and HIPAA authorization form to [contact].

Registration Process The patient registration process will be handled by the Department of Clinical Research Information Support (CRIS) Data Coordinating Center (DCC) at City of Hope. The steps below are to be taken when registering a **patient**:

- The research staff must assure they have the most current and updated version of the protocol and informed consent prior to enrolling a patient. If a question arises, please contact the Data Coordinating Center at [contact] [name] or via email at [contact].
- The study staff must assure that all prestudy laboratory tests, scans and x-rays have been completed prior to registration according to the study calendar
- The study staff must assure that the patient has signed an approved informed consent prior to registration/randomization, including the Experimental Subject Bill of Rights and appropriate HIPAA authorization.
- The study staff must confirm that the patient meets all inclusion and exclusion eligibility criteria for the protocol. The eligibility checklist (provided by the COH DCC) must be completed in its entirety.
- Patients must be registered prior to initiation of treatment but no more than 5 working days prior to planned start of treatment. A patient failing to meet all protocol requirements may not be registered.
- Once a patient is eligible, all the pre-study requirements have been fulfilled, and the informed consent obtained, the research nurse or the data manager (study coordinator) will inform the COH Data Coordinating Center at [contact], [name]; email [contact] and FAX ([contact]) a copy of the patient's signed informed consent, completed eligibility checklist and corresponding source documentation confirming eligibility (including pathology reports, lab reports, x-ray reports, etc.).

The City of Hope Data Coordinating Center will:

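### A Day 1 check given only to axitinib patients is worded as eligibility, so a man can be excluded from one arm after open-label randomisation, which conflicts with the intention-to-treat primary analysis

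*Combined protocol and SAP*

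**What the plan says.** **Before registration, both arms.** Inclusion criterion 3.1.10 requires "No evidence of preexisting uncontrolled hypertension as documented by 2 consecutive blood pressure readings taken within 1 hour", with systolic pressure at most 140 and diastolic at most 90. Section 5.1 adds "The study staff must confirm that the patient meets all inclusion and exclusion eligibility criteria for the protocol" and "A patient failing to meet all protocol requirements may not be registered". Registration is to happen "no more than 5 working days prior to planned start of treatment". Randomisation is item 4.1.2.10.

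**After randomisation, one arm.** The next block, 4.1.3, is headed "Pre-dose Assessments on Day 1 for patients randomized to axitinib". Its blood-pressure item, 4.1.3.2, reads "subjects must have a blood pressure reading of <140/90mmHg to be eligible". If antihypertensives were started or changed at baseline, it asks for two further readings, which must be the latest before treatment. Item 4.1.3.1 has the examiner look for changes "since baseline assessment that would make him/her ineligible for the study". For controls, Day 1 is the date of surgery, and no matching check is listed.

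**Consequence of failing.** Section 4.1 covers this case: "If a patient is randomized, but ultimately does not meet the eligibility criteria", he is a screen failure and does not take part. Section 5.1 allows a registration to be cancelled when protocol therapy is not received. Section 6.5 replaces axitinib patients who receive less than 75% of planned treatment.

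**Analysis.** Section 14.1.1 makes intention-to-treat primary, with the stated aim of an unbiased comparison. It does not define the population or mention men excluded between randomisation and first dose.

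**The concern.** The conduct rules and the analysis rule point in different directions. The man at issue passed every criterion at registration, was allocated to axitinib in an open-label trial, and then fails the Day 1 reading or examination. Sections 4.1 and 5.1 allow him to be taken out. Section 14.1.1 implies that he is analysed in his arm. A control whose pressure rose over the same days would not be re-tested and would stay.

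What is at stake is the protection given by randomisation. If the excluded men differ in niche density from those who stay, the axitinib mean shifts for a reason unrelated to the drug. The intention-to-treat label does not repair this, because the endpoint is counted in lymph-node tissue (9.1, 11.1) and nothing tells staff to assess the nodes of a man who has left the study.

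**Working it through.** **1. Order of events.**

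| Step | Section | Arm | Worded as |
|---|---|---|---|
| Baseline pressure, at most 140/90 | 3.1.10 | both | eligibility |
| All criteria confirmed, then registration | 5.1 | both | eligibility |
| Randomisation | 4.1.2.10 | both | – |
| Day 1 examination | 4.1.3.1 | axitinib | eligibility |
| Day 1 pressure, below 140/90 | 4.1.3.2 | axitinib | eligibility |
| Randomised but ineligible: out | 4.1 | both | exclusion |

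The exclusion rule in 4.1 applies to both arms. Only the scheduled re-test that can trigger it is one-sided.

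**2. The plan's own power figure.** Inputs from 14.1.1: means 3.13 and 2.19, SD 1.43, one-sided alpha 0.10, 22 per group, enlarged to 30 for 27% replacement.

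- Difference: 3.13 − 2.19 = 0.94.
- Noncentrality: 0.94 / (1.43 × √(2/22)) = 2.180, with 42 df and critical t 1.302. Power is 0.810, which agrees with the stated 80%.
- With 30 per arm: 0.94 / (1.43 × √(2/30)) = 2.546, with 58 df. Power is 0.894.
- 22 / (1 − 0.27) = 30.1. The number assessed could therefore lie anywhere from 22 to 30 per arm.

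**3. Harm from the plan as written.** The documents give no Day 1 failure rate and no relation between blood pressure and niche density, so this cannot be computed. As an illustration only, suppose one man is removed and he differs from the retained men by 0.25 to 1 SD. The arm mean moves by (1/n) × (0.25 to 1) × 1.43:

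- n = 30: 0.012 to 0.048 clusters, which is 1.3% to 5.1% of 0.94.
- n = 22: 0.016 to 0.065 clusters, which is 1.7% to 6.9% of 0.94.

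If removal is unrelated to density, the expected shift is zero.

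**4. Cost of keeping undosed men.** This is the price of the remedy and does not measure the harm. Assume k of the n axitinib men are undosed and the drug has no effect in them. Then:

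- difference = 0.94 × (n − k)/n
- axitinib variance = 1.43² + (k/n)(1 − k/n) × 0.94², pooled with the control variance of 1.43²

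For n = 30 and k = 1, the difference is 0.94 × 29/30 = 0.909 and the axitinib variance is 2.0449 + 0.0285 = 2.0734. The pooled SD is 1.435, the noncentrality 2.453 and the power 0.876.

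| Assessed per arm | k = 0 | k = 1 | k = 2 | k = 3 |
|---|---|---|---|---|
| 30 | 0.894 | 0.876 | 0.856 | 0.834 |
| 22 | 0.810 | 0.779 | 0.747 | 0.712 |

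If 22 per arm is the target and each undosed man is both replaced and kept, power is 0.787 with one (23 v 22) and 0.765 with two (24 v 22). With 30 assessed per arm, power is still 0.811 with four undosed.

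**The case against.** The strongest reply is that little is left to mend. Eligibility is settled in both arms before registration, so only a man who passes and then fails soon afterwards is affected. A raised baseline pressure is treated and re-measured (4.1.2.6, 4.1.3.2), which makes failures less likely. The cancellation line in 5.1 is permissive. Intention-to-treat ordinarily means analysis as randomised, and every participant already has a verified operative date (4.1.2.9), so his nodes could still be obtained. A pre-dose check is also sensible for a drug that raises blood pressure.

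Most of this stands, and it is why the point is a minor one. It does not remove the conflict. The plan has a stated rule that takes the man out, and the analysis label does not instruct anyone to assess his nodes. The follow-up provisions in 6.4, 7.0 and 7.1 concern men who discontinue or are removed from treatment. They cover PSA, tumour assessment and survival, and do not mention niche density.

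A reader might infer that the re-check should simply move ahead of randomisation in both arms, at no cost, because 5.1 already has eligibility confirmed close to treatment. The text does not support that. The limit of 5 working days in 5.1 applies to registration; the vital signs themselves may date from up to 2 weeks before the first dose (4.1.2). Moving the re-check could need extra measurements, and it would clash with the requirement that the two readings be the latest before treatment.

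**Conclusion.** The conflict is real and of low severity. Sections 4.1.3.1, 4.1.3.2, 4.1 and 5.1, followed as written, allow exclusion from the axitinib arm alone after open-label allocation, and 14.1.1 promises an intention-to-treat comparison. This rests on the wording and needs no numerical assumption.

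A reader might go further and infer that the primary result will be biased in favour of axitinib, or that its type I error is materially inflated. The documents do not support either. They give no failure rate, no direction and no association between blood pressure and niche density, so the bias is unquantified and may be near zero. The power figures above describe the remedy and rest on assumed counts and on no effect in undosed men.

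Two wording differences are clerical. The baseline limit includes 140 and 90 whereas the Day 1 limit excludes them, which matters only at exactly those values. The Day 1 re-check interval is within 1 hour in the synopsis but at least 1 hour in 4.1.3.2.

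**What to change.** 1. Reword 4.1.3.1, 4.1.3.2 and the matching synopsis text so that a Day 1 failure delays or withholds axitinib and leaves eligibility unchanged. Keep the two most recent pre-treatment readings as the dosing check. Section 7.1 already handles on-treatment hypertension by holding and restarting the drug.
2. Amend 4.1 and the cancellation line in 5.1 so that a man who was eligible at registration, and is undosed because of the Day 1 check, has his lymph nodes assessed at his planned surgery and is analysed in his randomised arm. State in 6.5 that a replaced man also stays in the intention-to-treat analysis.
3. Use one threshold and one re-check interval throughout; which to use is the sponsor's clinical choice.

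The first cost is slight dilution: the 0.94 difference falls to 0.94 × 29/30 = 0.91 with one of 30 undosed, or 0.94 × 21/22 = 0.90 with one of 22, with the power losses shown above. If only 22 per arm are assessed, one undosed man takes power below 80%. The second cost is practical. Section 6.1.1 times the axitinib start back from the surgery date, so a delayed start shortens the 28-day course unless surgery moves.

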5.0 Informed Consent

The investigational nature and objectives of the trial, the procedures and treatments involved and their attendant risks and discomforts, and potential alternative therapies will be carefully explained to the patient and a signed informed consent will be obtained.

5.1 Registration Requirements/Process

To register a patient, the treating physician should contact the protocol nurse or the responsible Clinical Research Associate (CRA) in Clinical Trial Office (CTO) to complete the eligibility/registration form. The protocol nurse or CRA will contact the Data Coordinating Center at the City of Hope [contact], [name] or e-mail [contact]), EMAIL a copy of the completed eligibility checklist, required pre-study tests (per protocol – and may include laboratory, CT and pathology reports), signed Informed Consent, signed Patients' Bill of Rights and HIPAA authorization form to [contact].

Registration Process The patient registration process will be handled by the Department of Clinical Research Information Support (CRIS) Data Coordinating Center (DCC) at City of Hope. The steps below are to be taken when registering a **patient**:

- The research staff must assure they have the most current and updated version of the protocol and informed consent prior to enrolling a patient. If a question arises, please contact the Data Coordinating Center at [contact] [name] or via email at [contact].
- The study staff must assure that all prestudy laboratory tests, scans and x-rays have been completed prior to registration according to the study calendar
- The study staff must assure that the patient has signed an approved informed consent prior to registration/randomization, including the Experimental Subject Bill of Rights and appropriate HIPAA authorization.
- The study staff must confirm that the patient meets all inclusion and exclusion eligibility criteria for the protocol. The eligibility checklist (provided by the COH DCC) must be completed in its entirety.
- Patients must be registered prior to initiation of treatment but no more than 5 working days prior to planned start of treatment. A patient failing to meet all protocol requirements may not be registered.
- Once a patient is eligible, all the pre-study requirements have been fulfilled, and the informed consent obtained, the research nurse or the data manager (study coordinator) will inform the COH Data Coordinating Center at [contact], [name]; email [contact] and FAX ([contact]) a copy of the patient's signed informed consent, completed eligibility checklist and corresponding source documentation confirming eligibility (including pathology reports, lab reports, x-ray reports, etc.).

The City of Hope Data Coordinating Center will:

- Review all materials/source documentation to ensure the patient is eligible.
- Ensure the consent form is valid and is signed correctly by all parties. If additional information is needed or should there be any questions, the Data Coordinating Center will immediately contact the participating institution and registration will not occur until all issues are resolved.
- If there are questions regarding exceptions to the eligibility criteria, please contact the study Principal Investigator, as well as the COH DCC. Documentation of IRB approval of exception will need to be submitted as well as the COH DCC.
- The patient will be registered and randomized centrally at City of Hope.
- Confirmation of Registration/Randomization will be emailed/faxed to the study staff noting the patient's study number as well as assigning the randomization arm within 24 hours post receipt of a complete eligibility packet.
- The COH DCC will call the research nurse or data manager (study coordinator) and verbally confirm the registration (if needed).

- If the patient does not receive protocol therapy following registration, the patient's registration on the study may be cancelled. The COH DCC should be notified of cancellations as soon as possible.
- The COH DCC will log into the Electronic Data Capture (EDC) system and enter the patient's study number.

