6.1.1 Schedule

In patients on the experimental arm, axitinib should be taken at a dose of 5 mg oral bid, with 28 days of therapy constituting 1 cycle.

The date of initiation of axitinib therapy will be contingent upon the date selected for prostatectomy and pelvic lymph node dissection, with 28 days of planned therapy to conclude 48 hours prior to surgical intervention.

In patients on the control arm, no systemic therapy will be instituted. Rather, prostatectomy and pelvic lymph node dissection will be carried out within 5-6 weeks after biopsy confirmation of prostate cancer.

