14.0 Statistical Considerations

14.1 Study Design

14.1.1 The study is an open label, randomized phase II assessment of axitinib as pre-surgical therapy in high risk prostate cancer. In particular, a permuted block randomization scheme will be carried out to achieve treatment/control balance. To avoid selection bias, the blocking scheme will be masked to the principal investigator. The number of blocks will be determined by stratifying high risk patients according to PSA levels (≥ 20 or not) and Gleason scores (≥ 8 or not). For each block, we will randomly choose one arrangement from all possible realizations.*Primary Endpoints*: The primary endpoint of this study is pre-metastatic niche density, as defined by the average number of VEGFR1 clusters in 8 distinct 40x microscopic fields. We will use a two sample student's T-test to compare the primary endpoint of pre-metastatic niche density in the regional lymph nodes of patients treated with axitinib, as compared to the pre-metastatic niche density in the lymph nodes of patients enrolled on the control arm. With a sample of 22 patients per group, we will have 80% power to determine significance across groups if the average niche density is 3.13 in patients in the control arm, and at most 2.19 in patients treated with axitinib, with a common standard deviation 1.43 using a one-sided t-test assuming a type I error = 10% (Calculated using nQuery Advisor 6.01) Taking this into consideration, 30 patients per group will be recruited according to an empirical replacement rate of 27%. The intention-to-treat analysis will be the primary analysis conducted to obtain unbiased comparisons between the treatment and control. In addition, some as-treated subgroup analysis would also be investigated if necessary.*Secondary Endpoints*: Toxicity, time to biochemical recurrence, time to metastatic recurrence. With respect to secondary endpoints, Cox regression will be used (with the log-rank test) to compare time to biochemical recurrence (PSA ≥ 0.2), TTP and OS in patients treated with axitinib to patients treated with surgery alone. The Chi-square test will be used to compare the pStat3, LOX expression and MDSC density in patients treated with axitinib to patients treated with surgery alone. Descriptive statistics will be used to compare serum levels of VEGF-A, sVEGFR2, PDGF-AB and pSTAT3 at various timepoints during therapy.

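### Section 5.1 lets a registration be cancelled after the arm is known, and nothing in the plan keeps the cancelled man in the primary intention-to-treat comparison

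*Combined protocol and SAP*

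**What the plan says.** **Order of events (section 5.1).** "The patient will be registered and randomized centrally at City of Hope". The confirmation then goes to study staff, "noting the patient's study number as well as assigning the randomization arm within 24 hours post receipt of a complete eligibility packet". The cancellation rule follows: "If the patient does not receive protocol therapy following registration, the patient's registration on the study may be cancelled". On timing: "Patients must be registered prior to initiation of treatment but no more than 5 working days prior to planned start of treatment".

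**Blinding and analysis (section 14.1.1).** "The study is an open label, randomized phase II assessment of axitinib as pre-surgical therapy in high risk prostate cancer". "The intention-to-treat analysis will be the primary analysis conducted to obtain unbiased comparisons between the treatment and control". The section mentions as-treated analyses as possible additions. It does not say who belongs to the intention-to-treat set.

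**What each arm receives.** Section 6.1.1: "In patients on the control arm, no systemic therapy will be instituted". Section 6.6.4 treats prostatectomy and pelvic node dissection as mandated. The note in section 4.1.3 says "Day 1 for patients randomized to observation will represent the date of surgical intervention". The plan does not define protocol therapy. The synopsis uses a similar phrase for axitinib.

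**Related rules.** Section 4.1 treats a randomised man who proves ineligible as a screen failure who takes no part. Section 6.5 replaces men who receive less than 75% of planned axitinib. Section 14.1.1 raises 22 per arm to 30 for a 27% replacement rate.

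**The concern.** A man can be taken off the study after allocation, by people who know his arm, under a rule that says he may be cancelled and gives no criteria. If cancellation also means that his nodes are not scored and his PSA is not followed, the arms compared are no longer the arms randomised.

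Non-starting is foreseeable mainly in the axitinib arm. The Day 1 checks in section 4.1.3, including a blood pressure limit, apply after randomisation and only to men assigned axitinib. Men who do not pass them, or who decline the drug, need not resemble those who start. Both the niche-density comparison and the recurrence comparison could be affected. Section 6.4 continues PSA measurement for men taken off study treatment, but it does not clearly cover a man who never started and was cancelled.

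**Working it through.** **1. Reproduce the design.** Inputs from section 14.1.1: means 3.13 and 2.19, SD 1.43, one-sided alpha 0.10, 22 per group.

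- Difference = 3.13 − 2.19 = 0.94; 0.94/1.43 = 0.657 SD.
- Noncentrality = 0.94 / (1.43 × √(2/22)) = 0.94/0.431 = 2.18 on 42 degrees of freedom. Noncentral-t power is 0.810 (0.796 with 21 per group). The stated 80% with 22 reproduces.
- 22/(1 − 0.27) = 30.1, stated as 30; 30 × 0.73 = 21.9. The plan therefore expects about 22 of 30 to remain in each arm.

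**2. Whom does the rule reach?**

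| Meaning of protocol therapy | Axitinib non-starter who has surgery | Control who has surgery | Control without surgery |
|---|---|---|---|
| Study drug | can be cancelled; has nodes | can be cancelled (every control could) | can be cancelled |
| Treatment assigned to the arm | can be cancelled; has nodes | cannot be cancelled | can be cancelled; no nodes |

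The first reading cannot be intended. Under the second, the only men with an observable primary endpoint who can be cancelled are axitinib non-starters.

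**3. Effect on type I error if they are dropped.** Assumptions, none given in the documents: no drug effect; k of 30 axitinib men dropped; their mean density differs from that of the retained men by m SD; all 30 controls analysed; SD held at 1.43. The retained axitinib mean then moves by (k/30) × m × 1.43. For k = 3 and m = 0.5 this is 0.10 × 0.5 × 1.43 = 0.07, or 7.6% of 0.94. The upper value, k = 8, is 27% of 30. The error is the noncentral-t rejection probability with 30 − k against 30.

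| k | m | Shift | Error if dropped men are denser | Error if less dense |
|---|---|---|---|---|
| 3 | 0.25 | 0.036 | 0.117 | 0.085 |
| 3 | 0.5 | 0.071 | 0.137 | 0.071 |
| 3 | 1.0 | 0.143 | 0.182 | 0.049 |
| 8 | 0.25 | 0.095 | 0.148 | 0.065 |
| 8 | 0.5 | 0.191 | 0.209 | 0.040 |
| 8 | 1.0 | 0.381 | 0.367 | 0.013 |

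With m = 0 the error stays at 0.10 and only sample size is lost.

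**4. Cost of keeping them.** Assume that k of 30 never start, all have surgery, and their density is like that of controls. The effect becomes 0.94 × (1 − k/30), tested 30 against 30.

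| k | Effect | Power |
|---|---|---|
| 1 | 0.91 | 0.877 |
| 3 | 0.85 | 0.840 |
| 4 | 0.81 | 0.818 |
| 5 | 0.78 | 0.795 |
| 6 | 0.75 | 0.771 |
| 8 | 0.69 | 0.716 |

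**The case against.** The strongest defence is that section 5.1 concerns registration and says nothing about analysis sets, while section 14.1.1 governs the analysis and names intention-to-treat as primary. On a conventional understanding the cancelled man would stay in. It is fair that his removal from the analysis is inferred. But no section says that he stays, and the post-randomisation screen-failure rule, the replacement rule and the 27% allowance all make exclusion the likely practice.

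A reader might infer that only axitinib men can be cancelled. The text does not support this: protocol therapy is undefined, surgery is mandated in both arms, and it is the controls' Day 1. A control who misses surgery could be cancelled too, although he would have no nodes to score.

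A reader might also take this as wholly separate from section 6.5, on the view that the 75% rule covers only men who start. Section 6.5 has no such limit, and a man who receives none of the drug falls below 75%. A man stopped by the Day 1 blood pressure check may leave as a screen failure under section 4.1 instead. So the three rules overlap, which is a reason to settle them together.

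Finally, some non-starters will not have surgery. Section 3.1.11 has men offered a radiation consultation, and some may choose that treatment. Cancelling such a man does not change the node comparison. The window of at most 5 working days before planned treatment also limits the opportunity for non-starting. Both points reduce the likely number but do not remove the problem.

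**Conclusion.** The concern holds in a limited form. Section 5.1 permits a discretionary exclusion after randomisation with the arm known, and section 14.1.1 does not protect the primary comparison against it. The exposure is greatest for axitinib non-starters who go on to surgery. It should be corrected, but it does not show that the result will be biased.

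It would go too far to say that the plan directs the deletion of these men from the intention-to-treat analysis, or that the test is known to be anti-conservative. The size rests on a non-starter rate and a density difference that the documents do not give. With 3 of 30 dropped and differences of 0.25 to 1 SD, the nominal 0.10 becomes 0.117 to 0.182 if the dropped men are denser, and 0.085 to 0.049 if they are less dense. With no difference there is no bias.

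**What to change.** One sentence in section 5.1 is not enough, because it would conflict with section 4.1 and leave section 6.5 unreconciled.

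- **Section 5.1:** allow cancellation only before randomisation, and define protocol therapy for each arm.
- **Section 14.1.1:** define the intention-to-treat set as all randomised men, by assigned arm. State that cancellation, replacement under section 6.5 or failure to start does not remove a man from it. Exclude non-starters only from the as-treated analysis.
- **Section 4.1:** reconcile the screen-failure rule with that definition, including for men who do not pass the axitinib-only Day 1 checks.
- **Data collection:** for non-starters who have surgery and have not withdrawn consent, score the nodes and continue PSA follow-up.
- **Missing endpoint:** state how men without nodes are handled, with numbers and reasons by arm.
- **Reporting:** give cancellations and non-starters by arm.

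The cost is a short text change; the slides and assays are already planned. The statistical price is dilution. Under the assumptions in step 4, power at 30 per arm stays near 80% up to about 4 to 5 non-starters and is about 0.77 with 6. These figures use the 60 patients of section 14.2, whereas the synopsis gives 44. That difference is a separate matter, but it must be settled before the margin can be relied on.
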